### 1. SYNOPSIS

Sponsor	CytoSorbents Corporation
Title	CytoSorb ® REduction of FREe Hemoglobin/Acute Kidney Injury (AKI) during Cardiac Surgery (REFRESH II Trial)
Study device	CytoSorb ® is a sorbent-filled hemoperfusion cartridge that is designed to reduce plasma free hemoglobin (pfHb) and other inflammatory mediators from blood that are generated during cardiopulmonary bypass in cardiac surgery.
Purpose of study	
 
To evaluate the safety and performance of the CytoSorb® device to
 
decrease the incidence or severity of acute kidney injury (AKI) as defined
 
by Kidney Disease Improving Global Outcomes (KDIGO) clinical
 
practice guideline definition of acute kidney injury when used
 
intraoperatively with cardiopulmonary bypass (CPB) in subjects
 
undergoing cardiac surgery. The objective of using CytoSorb® treatment
 
in this setting is to provide clinically meaningful improvements in renal
 
function by mitigation of intraoperative injury by removal of nephrotoxic
 
agents such as pfHb and complement.
 

Study design	
 
Prospective, multi-center, randomized, pivotal double-blinded clinical study. Subjects will be randomized in a 1:1 ratio to either standard of care (SOC) alone or standard of care plus treatment with the CytoSorb® device, with or without HCA. The number of patients with and without HCA will be assessed in the interim analysis.
 
Interim analyses will be carried out for potential (NON-BINDING) early stopping for an efficacy or futility conclusion.
 
An option to increase sample size (SSR, i.e., Sample Size Re-estimation) will be considered. SSR is based on the second interim analysis (IA) results using the conditional probability (CP) to estimate the sample size necessary to boost the CP to 88%, assuming the observed response proportions are the TRUE underlying proportions.
 
To assure proper startup of the sites we will employ a roll in approach for up to the first two enrolled and treated subjects from each site for training. The roll in subjects will be treated with the CytoSorb® device. The data will be used for safety analysis only.
 

Study Population	
 
The population evaluated for effectiveness in the treatment group will consist of a primary sub-population and a secondary sub-population.
 
The primary sub-population includes all subjects enrolled and randomized to the treatment group who are undergoing valve replacement with another procedure (e.g., CABG and valve replacement) without Hypothermic Circulatory Arrest (HCA)
 
The secondary sub-population consists of all surgical subjects undergoing aortic reconstructions with or without other procedures (e.g., CABG, valve replacement) with HCA
 

Sample Size	40 investigational sites in the United States. A roll-in cohort of up to 80 additional subjects may be enrolled in the study and assigned to treatment with CytoSorb device.
Duration of participation for each patient	Primary, secondary, and exploratory endpoints will be evaluated on the day of cardiac surgery up to Day Seven (7) post-cardiac surgery or through hospital discharge, whichever occurs first. Subjects will be followed through 30-day follow-up visit to fully evaluate safety (AEs will be followed through study exit and device-related SAEs will be followed until a return to a stable state as determined by the investigator).
Patient treatment	Two devices, configured into a parallel circuit are placed between the oxygenator and the venous reservoir and run as a bypass shunt to the main blood flow in a standard heart-lung machine. The first device will be introduced at t=0 (start of CPB). The second device will be introduced at t=90 minutes after the start of CPB.
Study Objectives:	To evaluate the safety and performance of the CytoSorb ® device to decrease the incidence or severity of AKI in the first 48 hours after surgery when used intraoperatively with cardiopulmonary bypass (CPB) in subjects undergoing cardiac surgery. The study hypothesis is that, for patients at increased risk for AKI based upon use of the Cleveland Clinic Score for stratification of the risk of cardiac surgery associated AKI (CSA-AKI), the intra-operative usage of the CytoSorb ® device in addition to the standard of care in a bypass circuit during cardiopulmonary bypass will decrease the incidence or severity of AKI per the Kidney Disease Improving Global Outcomes (KDIGO) clinical practice guideline definition of acute kidney injury.
Primary Effectiveness Endpoint	The primary effectiveness endpoint is the incidence or severity of AKI in the first 48 hours after surgery when used intraoperatively with cardiopulmonary bypass (CPB) in subjects undergoing cardiac surgery as

	defined by the KDIGO clinical practice guideline through 48 hours post- cardiac surgery. Assessment of serum creatinine and hourly measurements of urine output will be recorded for the first 48 h following admission to the ICU. The intended primary effectiveness sub-population includes all subjects enrolled and randomized to the treatment group who are undergoing valve replacement with another procedure (e.g., CABG, valve replacement) without Hypothermic Circulatory Arrest (HCA). Balance between patients undergoing cardiac surgery with and without HCA will be evaluated during the interim analysis and the primary sub-population confirmed.
Primary Safety Endpoint	The primary safety endpoint of this trial is to evaluate the product safety profile through the assessment of device related adverse events during the study period.
Secondary Effectiveness Endpoints	
 
Secondary effectiveness endpoints include the following:
 
Change from baseline (defined as the start of CPB) in pfHb assessed hourly for the duration of CPB and at the end of CPB;
 
Change from baseline (defined as start of CPB) in Complement 3a (C3a) assessed hourly for the duration of CPB and at the end of CPB;
 
Severity of AKI through hospital discharge or post-surgical Day 7, whichever is sooner:
 
Incidence of AKI through hospital discharge or post-surgical Day 7, whichever is sooner:
 
Change from baseline (defined as pre-procedure) in serum creatinine through hospital discharge or post-surgical Day 7, whichever is sooner;
 
Additionally, the following pharmacoeconomic endpoints are included:
 
Duration of hospital stay, post-surgery
 
Duration of renal replacement therapy, post-surgery
 
Duration of vasopressor use, post-surgery
 
Duration of ventilator use, post-surgery
 

Secondary Safety Endpoints	
 
Secondary safety endpoints include the following:
 
Incidence and severity of procedure-related adverse events, through 30-days post-cardiac surgery.
 
Incidence of Serious device-related adverse events
 

	
 
Incidence and severity of unanticipated adverse device effects (UADEs)
 

		tomography, magnetic resonance imaging or angiography
		performed within 90 days prior to surgery (II $LVEF \le 35\%$
		meets the risk factor):
		e. Insulin-requiring diabetes:
		f. Non-insulin-requiring diabetes AND the presence of $\geq +2$
		proteinuria on urinalysis (medical history or dipstick);
		g. Pre-operative anemia (hemoglobin < 11g/dl)
		h. BMI $\geq$ 30 kg/m2
Exclusion Criteria	1.	Weight < 99 lbs. or > 383 lbs.;
	2.	The presence of AKI (KDIGO criteria) at the time of screening;
	3.	eGFR < 30 ml/min/1.73m  ;
	4.	Prior organ transplantation;
	5.	Dialysis dependence;
	6.	Cardiogenic shock or hemodynamic instability within 48 hours prior
		to surgery as defined by a systolic BP $< 80 \text{ mm Hg and pulse} > 120$
		beats per minute (bpm) and requirement for inotropes or
		counter-pulsation (IABP): or extracorporeal membrane oxygenation
		(ECMO). Short term vasopressor support is allowed during
		induction; however, ongoing requirement for vasopressor support to
		the time initiation of CPB would be excluded;
	7.	Requirement for any of the following within seven (7) days prior to cardiac surgery:
		a. defibrillator or permanent pacemaker,
		b. mechanical ventilation,
		c. intra-aortic balloon counter-pulsation (IABP),
		d. left ventricular assist device (LVAD),
		e. other forms of mechanical circulatory support (MCS) such as extracorporeal membrane oxygenation (ECMO);

8.	Cardiopulmonary resuscitation within 14 days prior to cardiac
	surgery;
9.	Known or history of inadequately treated cancer within the past 5
	years. Inadequately treated cancer is defined as the continued
10	Known on sugmented cancil at time of sensoring on within the 20 days
10.	prior to cardiac surgery.
11.	Known or suspected glomerulonephritis or interstitial nephritis at
	time of screening;
12.	Untreated endocarditis; however, successfully treated endocarditis,
	defined as having completed a full course of antibiotics with no
	evidence of recurrence of infection, is acceptable;
13.	Other current active infection requiring antibiotic treatment including
	Hepatitis B (HBV), Hepatitis C (HCV) or human immunodeficiency
	virus (HIV) infections. Documented inactive HBV and HCV are
	regimen for a minimum of 30 days prior to the date of surgery:
14	Any other clinically relevant finding or medical history that based
17.	upon the determination of the Investigator, may introduce additional
	risk to the patient or confound the results of the study;
15.	Use of stress dosed steroids at the time of surgery,
	immunosuppressant medications to prevent transplant rejection or
	immunosuppressant chemotherapeutic agents;
16.	Presence of acute or chronic pancreatitis;
17.	Patients known to have Child-Pugh Class A Liver disease or with
	alanine aminotransferase (ALT) or aspartate aminotransferase (AST)
	> 2 times the Upper Limit of Normal (ULN);
18.	Any congenital coagulation disorder;
19.	Pregnancy or lactation;
20.	Treatment with an investigational drug or device within 60 days
	prior to surgery;
21.	Inability to comply with the requirements of the study protocol;
22.	Subject has a platelet count of $< 50,000 / \mu L$ .

### Table 1: Definitions

Arterial Blood Gas Assessments	Intra-procedure, while patient is on CPB Post-Procedure, only if arterial line is in place
Enrolled	A patient who has provided informed consent to participate in the trial is considered to be enrolled.
Roll-in	The first two enrolled and treated patients at each site used for training purposes. Roll in patients are treated with the CytoSorb device and their data used for safety analysis only.
Randomized	A patient who has been randomly assigned (according to a validated randomization schedule) in a 1:1 ratio to either standard of care (SOC) or SOC with CytoSorb device.
Intra-Cardiac Procedure	During CPB, while on pump
Post-Cardiac Procedure	Following end of CPB
Pre-Procedure	Day of the surgery but before induction of general anesthesia, exclusive of sedation.
Screening	Time-period to determine eligibility, not more than 14 days prior to day of cardiac surgery. When screening laboratory assessments are obtained on the day of surgery, they may be substituted for the pre-procedure laboratory assessments
Baseline	The start of CPB is defined as baseline for pfHb, C3a, C5a, inflammatory mediator panel, and markers of kidney injury (plasma and urine markers) endpoints.
	Pre-procedure is defined as baseline for all other endpoints.
Start Of CPB	Pump on
End Of CPB	Pump off, just prior to protamine reversal ( $\pm$ 5 minutes)
Post-Surgery Care Unit	Coronary Care Unit, Intensive Care Unit, Step Down Unit
Post-Surgery Care Unit Assessments and Labs	Day 1 assessments start at or after midnight post-cardiac surgery. Assessments and lab blood draw times should be approximately the same time each day (see Schedule of Assessments for specific assessments and labs, as well as approved windows).

Abbreviation/Term	Definition
ABG	Arterial blood gas
ADL	Activities of Daily Living
AE	Adverse Event
AKI	Acute kidney injury
ALT	Alanine aminotransferase
APTT	Activated partial thromboplastin time
ARDS	Acute respiratory distress syndrome
AST	Aspartate aminotransferase
AUC	Area under the concentration by time curve
BP	Blood pressure
C3a	Serum complement component C3a
C5a	Serum complement component C5a
CABG	Coronary artery bypass graft
CFR	Code of Federal Regulations
CKD	Chronic kidney damage
СРВ	Cardiopulmonary bypass
CRF	Case Report Form
CRO	Contract research organization
CRP	C-reactive protein
DMC	Data monitoring committee
DMP	Data management plan
ECG	Electrocardiogram
ECMO	Extracorporeal membrane oxygenation
eCRF	Electronic case report form
EDC	Electronic data capture
ESRD	End-stage renal disease
FDA	US Food and Drug Administration
FIO 2	Fraction of inspired oxygen
GCP	Good Clinical Practice
HB	Hemoglobin
HCA	Hypothermic Circulatory Arrest
HLM	Heart-lung machine
HMGB1	High mobility group box protein 1

Abbreviation/Term	Definition
HR	Heart rate
IABP	Intra-aortic balloon
ICH	International Conference on Harmonization
ICU	Intensive care unit
IDE	Investigational Device Exemption
IGFBP7	Insulin-like growth factor binding protein 7
INFG	Interferon Gamma
IL-2	Interleukin 2
IL-4	Interleukin 4
IL-5	Interleukin 5
IL-6	Interleukin 6
IL-10	Interleukin 10
IL-12	Interleukin 12
INR	International normalized ratio
IRB	Institutional Review Board
KDIGO	Kidney Disease: Improving Global Outcome group
NGAL	Neutrophil gelatinase-associated lipocalin
NYHA	New York Heart Association
OUS	Outside of the US
paC0 2	Partial pressure of carbon dioxide
paO 2	Partial pressure of oxygen
PEEP	Positive end-expiratory pressure
pfHb	Plasma free hemoglobin
РТ	Prothrombin time
RBC	Red blood cell
SAE	Serious adverse event
SCr	Serum creatinine
SOC	System organ class
SOFA	Sequential Organ Failure Assessment Score
SOP	Standard operating procedure
TIMP-2	Tissue inhibitors of metalloproteinases
TNF-α	Tumor necrosis factor alpha
UADE	Unanticipated adverse device effect

Abbreviation/Term	Definition
US	United States
VAD	Ventricular assist device
WBC	White Blood Cell

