### 3.5 Investigational Device Procedure(s)/Training

The CytoSorb® device is designed for use in a standard heart-lung machine CPB circuit with an arterial pump. In this study, as described in the Instructions for Use (IFU), up-to two CytoSorb® cartridges in a parallel configuration will be in a bypass circuit connected between the oxygenator and cardiotomy reservoir as shown in **Figure 2**, and separate from the main blood flow to the subject. Blood flow through this circuit is controlled via an adjustable roller clamp distal to the cartridges and monitored via ultrasonic flow detection to maintain flow. A minimum blood flow of ~ 300 ml through the single device, or ~ 600 ml through the paired devices together is acceptable.

The circuit containing the CytoSorb® devices will be connected prior to the start of the procedure. Blood flow through the first CytoSorb® device will commence when subject goes on CPB. Flow through the second CytoSorb® device will commence at 90 minutes from the start of CPB (at this time both CytoSorb® devices will have blood flowing through them). Use of the CytoSorb® devices is stopped at the end of CPB. Once the CPB procedure is complete the hemoperfusion session will be ended, the circuit is flushed with saline, with the return of blood in the circuit back to the subject, per the hospital protocol.

CytoSorb® device training for the device users involved in this study will occur prior to CytoSorb® device use and will be documented in a training log.

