#### 6.3.4 Secondary Effectiveness Endpoint(s)

Secondary effectiveness endpoints include the following:

- Change from baseline (defined as the start of CPB) in pfHb assessed hourly for the duration of CPB and at the end of CPB;
- Change from baseline (defined as start of CPB) in Complement 3a (C3a) assessed hourly for the duration of CPB and at the end of CPB;
- Severity of AKI through hospital discharge or post-surgical Day 7, whichever is sooner
- Incidence of AKI through hospital discharge or post-surgical Day 7, whichever is sooner
- Change from baseline (defined as pre-procedure) in serum creatinine through hospital discharge or post-surgical Day 7, whichever is sooner;

Additionally, the following pharmacoeconomic endpoints are included:

- Duration of hospital stay, post-surgery
- Duration of ICU stay, post-surgery
- Duration of renal replacement therapy, post-surgery
- Duration of vasopressor use, post-surgery
- Duration of ventilator use, post-surgery

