## 8.5.3 Procedure (CPB Surgery)

### 8.5.3.1 Treatment Arm

Subjects randomized to the treatment arm will receive standard of care bypass plus treatment with one CytoSorb® device at the beginning of CPB. If and when CPB continues for more than 90 minutes of bypass time, a second (parallel configuration) device will be opened to the bypass circuit. Treatment with the CytoSorb® device(s) will continue until the end of CPB. Blood flow is to be maintained continuously through the CytoSorb® devices.

As per the instructions for use (IFU), prior to hemoperfusion, prime and flush the circuit with saline or crystalloid solution and prevent any air from entering into the system and clamp

lines. During this phase, gently tap the CytoSorb® device to liberate any trapped air. Also, for a short period, the pump speed can be increased to allow for clear identification of any possible leaks at the increased pressure/flow rate. Hemoperfusion with CytoSorb® will begin at the commencement of CPB flow to the subject.

CytoSorb® treatment flow rates will be controlled utilizing a roller clamp placed just beyond the junction of the outlet-side Y-tube. The flow rate will be measured using a Sponsor provided Transonic (or equivalent) ultrasonic flow meter and probe, also placed just beyond the junction of the outlet-side Y-tube. The blood flow rate of the device will be adjusted to yield an initial target reading of ~400 ml/min (minimum above 300 ml/min is acceptable) measured beyond the junction of the outlet-side Y-tube. If/when CPB goes beyond 90 minutes and the second, parallel CytoSorb unit is brought into play 90 minutes into CPB by opening its C-clamp, total flow should be adjusted to yield a target flow rate of ~800 ml/min (minimum of 600 ml/min is acceptable), as measured beyond the junction of the outflow "Y" tube. Because of the parallel nature of the circuit, when using both CytoSorb units, this will equate to a target flow rate of ~400 ml/min through each device, with an acceptable lowest flow rate of 300 ml/min per device.

Throughout the treatment session, monitoring the CytoSorb device for blood leaks, pressure spikes or clots is essential. Any adverse device events and/or device observations must be recorded by indicating the location of leaks or by recording the size of clots present.

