### 8.5.3.2 Control Arm

Subjects randomized to the control arm will receive standard of care bypass at the beginning of CPB.

The following procedures will be performed, and results recorded in the eCRF:

• Eligibility based on inclusion / exclusion criteria will be confirmed. Subjects who meet all inclusion and exclusion criteria will be randomized to either the control arm or to the treatment arm

- Vital signs
- Sequential Organ Failure Assessment (SOFA) score will be assessed before induction of anesthesia;
- Initiate recording of fluids administration (e.g. crystalloids)
- Initiate recording of supplementation with calcium and/or albumin
- Blood samples will be drawn for the following assessments:
  - Hematology
  - Coagulation panel
  - Comprehensive metabolic panel
  - o ABG
  - Ionized Calcium
  - ACT (per SOC)
  - Serum creatinine
  - Complement C3a and C5a
  - Inflammatory mediator panel
  - Kidney injury markers urine: urine NGAL, IGFBP7, TIMP2);
  - Kidney injury markers plasma: HMGB1 and Cystatin C;
  - Plasma free hemoglobin (pfHb);

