### Table 3: Schedule of Assessments

		1	Procedure (CP	B/Surgery)			Post-Surgery period	Discharge	Follow-up	
Event	Screening 	Pre-Procedure (before induction of general anesthesia)	Start of CPB (±5 minutes)	Hourly while on CPB (±5 minutes)	End CPB (post protamine)	Admission to Post- Surgery Care unit (+1 hour)	Daily for Post day 1-3 Post-Cardiac Surgery or Hospital Discharge (whichever is sooner) 	Day 4-7 Post- Cardiac Surgery	Hospital Discharge	30 Day Follow-up (±5 days)
Informed Consent	Х									
Demographics, Height	X									
Weight	X	Х				X	Х	Х		
Medical History	X									
Prior Medications (taken within 60 days of Screening Visit)	X									
Concomitant Medications – inclusive of IV contrast media administered within 48 h of procedure			As Needed							
Inclusion/Exclusion Criteria (w/in 14 days of surgery)	X									
Inclusion/Exclusion Review		Х								
Vital Signs (HR, BP, Temp) 	X	Х			Х	X	Х	Х		
New York Heart Association (NYHA)	X									
Echocardiogram (Ejection Fraction) 	X									
Estimated Glomerular Filtration Rate (eGFR)	X									
Physical Examination	X									
SOFA Score (includes FiO2, level of hypotension assessment, evaluation of		X 				X 	X 		X 	

		Procedure (CPB/Surgery)					Post-Surgery period	Discharge	Follow-up	
Event	Screening 	Pre-Procedure (before induction of general anesthesia)	Start of CPB (±5 minutes)	Hourly while on CPB (±5 minutes)	End CPB (post protamine)	Admission to Post- Surgery Care unit (+1 hour)	Daily for Post day 1-3 Post-Cardiac Surgery or Hospital Discharge (whichever is sooner) 	Day 4-7 Post- Cardiac Surgery	Hospital Discharge	30 Day Follow-up (±5 days)
mechanical ventilation and vasopressor requirement, MAP, Glasgow Coma Score) 										
Randomization		$X^4$								
Vasopressor Requirements 				Х	Х	X	X	Х	X9	
FiO 2 (if patient is intubated on mechanical ventilatory support)		X	Х		X	X	X	Х		
Start/Stop Times of CytoSorb Treatment & Flow rate every 30 minutes (Treatment arm only)			X	X	Х					
Blood Product Transfusions 			Х	Х	Х	X	X	Х	X	Х
Ventilation & Mechanical support Requirements						X	X	Х	X	
Renal Replacement Requirements						X	X	Х	X	
Type of Surgical Procedure(s)					Х					
Administration of fluids is recorded 		X						X		
Supplementation with Ca and/or Albumin 		X						X		

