Event	Screening 	Pre-procedure Day of surgery but before induction of anesthesia	Start of CPB (±5 min)	Hourly while on CPB (±5 min)	90 minutes after Start of CBP Start of Device # 2) (±5 min)	End CPB  Off pump and post protamine	Admission to post- surgical care unit (+ 1 h)	Post- surgical Days 1-3	Post- surgical Days 4-7 or discharge, whichever is sooner	Hospital Discharge	30-day Follow up (±5 days)
Pregnancy Test 	Х										
Hematology 	X	X 				X	X	Х	SOC	Х	
Coagulation 	Х	X 				X	X	SOC	SOC	Х	
Comprehensive Metabolic Panel 	Х	X 				X	X	Х	SOC	Х	
Serum Creatinine 	X	X 				X	X	Х	X	Х	
Complement C3a & C5a		X	Х	X		X	X	Х			
Arterial Blood Gases  (includes PaO 2 , PaCO 2 , pH, HCO 3 )		SOC	SOC	SOC		SOC	SOC	SOC			
Ionized Calcium, Total Serum Calcium, Serum Albumin		X	Х	X		X	X	Х			
Activated Clotting Time (ACT) 		SOC	SOC	SOC		SOC	SOC				

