### 11.1.2 Effectiveness evaluations:

The primary endpoint will be assessed in each modified intent-to-treat (mITT) population in step-wise fashion beginning with the primary sub-population. If a significant beneficial effect is met for CytoSorb over control at a one-sided overall 0.025 level of significance, then the study will be considered to be a primary endpoint statistical success on this subpopulation and testing will proceed to the secondary sub-population. Otherwise the study will be considered to have statistically failed the primary endpoint.

We have selected to use a modified intent-to-treat population (mITT) population to avoid the consequence of including patients that were excluded from the study after randomization due to administrative reasons.

Use of the mITT population as defined is not anticipated to result in bias or informative censoring of the data.

The primary endpoint (rank order presence and severity of AKI) will be compared between treatments with Wilcoxon Rank Sum test. Continuous endpoints will be assessed via ANCOVA with baseline value as covariate. Binary endpoints will be assessed via unconditional exact binomial test. The primary endpoint will be summarized by subgroup factors, e.g., those who receive IV contrast within 48 hours prior to surgery versus those who do not. Additionally, subgroup-by-treatment interaction may be tested via generalized ordered categorical model and/or for binary combinations of outcomes (e.g., presence / absence of any AKI, and/or severe AKI) by logistic regression. Details will be in the SAP.

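### The start-of-CPB baseline for pfHb, C3a, C5a and the mediator panel can be drawn after device flow has begun in the treated arm only

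*Protocol*

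**What the plan says.** **Baseline.** Protocol Table 1 gives: "The start of CPB is defined as baseline for pfHb, C3a, C5a, inflammatory mediator panel, and markers of kidney injury". The same table defines start of CPB as pump-on. (The kidney injury markers in that sentence are left aside here, because Table 4 schedules no start-of-CPB sample for them.)

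**Window.** The relevant column of Table 3 is headed "Start of CPB (±5 minutes"; Table 4 uses the same window. The start-of-CPB sampling lists in 8.5.3.1 and 8.5.3.2 do not require the draw to precede pump-on or device flow.

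**Device start.** In the treated arm, section 3.5 says flow through the first "device will commence when subject goes on CPB", and section 8.5.3.1 says hemoperfusion "will begin at the commencement of CPB flow to the subject". The control arm has no device: "Subjects randomized to the control arm will receive standard of care bypass at the beginning of CPB" (8.5.3.2).

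**Use of the baseline.** Section 6.3.4 defines a secondary endpoint as "Change from baseline (defined as the start of CPB) in pfHb assessed hourly for the duration of CPB and at the end of CPB", with a parallel one for C3a. Section 6.3.5 does the same for C5a and the mediator panel as exploratory endpoints. Section 11.1.2 adds: "Continuous endpoints will be assessed via ANCOVA with baseline value as covariate".

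**An earlier sample.** Section 8.5.2 and Table 4 already schedule pfHb, C3a, C5a and the mediator panel before induction of anesthesia. That value is not used as their baseline.

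**The SAP.** SAP v1.0 was written after the sponsor stopped the study at 151 of 420 planned subjects (4.1). It contains no ANCOVA and no analysis of these markers; its secondary efficacy section (6.7.2) lists only health-economic items.

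**The concern.** A baseline should be untouched by the randomised treatment. Here sampling window and device start share the same zero, so a draw that complies with the protocol can be a post-treatment value in one arm and not in the other. If the device removes the marker, the treated baseline is lowered, and both subtracting it and adjusting for it hide part of the effect. A larger sample would not remove this.

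These endpoints matter because section 4 of the protocol presents pfHb and complement removal as the test of the device's mechanism. That section also explains how the overlap arises. In REFRESH I the devices were introduced 1 hour after the start of CPB, so under that schedule a start-of-CPB draw would precede treatment. REFRESH II moves the first device to time zero, expressly so that adsorption begins with bypass.

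**Working it through.** The plan gives no power, SD or effect size for these markers, so there is no stated figure to reproduce.

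**1. Exposure at the end of the window, from the documents' own figures.** Single-device flow is about 400 mL/min, with about 300 mL/min acceptable (8.5.3.1), and the window ends at +5 minutes.
- 0.3 L/min × 5 min = 1.5 L
- 0.4 L/min × 5 min = 2.0 L
- Control: 0 L. Any draw before pump-on: 0 L in both arms.

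**2. Fraction removed at exactly +5 minutes, on assumed inputs.** Neither single-pass extraction E nor distribution volume V is in the documents. Take E = 10-50% and V = 5-8 L, with one well-mixed compartment and a constant 0.4 L/min from time zero. The fraction removed is 1 − exp(−2.0 × E / V).
- E = 0.1, V = 8: 1 − exp(−0.025) = 2.5%
- E = 0.3, V = 6.5: 1 − exp(−0.092) = 9%
- E = 0.5, V = 5: 1 − exp(−0.2) = 18%

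**3. Average over the window, if draws are uniform over ±5 minutes (also assumed).** Half the draws have no exposure. With x = 2.0 × E / V, the treated-arm average is ½ × [1 − (1 − exp(−x)) / x].
- x = 0.025: 0.6%
- x = 0.092: 2.2%
- x = 0.2: 4.7%

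**4. Effect on the estimate.** Work in SD units with equal SDs at both times. Let τ be the true later effect, ρ the baseline-outcome correlation, and d the mean lowering of the treated baseline. The true baseline equals the recorded one plus d in the treated arm, so:
- ANCOVA estimates τ + ρd. The result is the same whether the outcome is the later value or the change.
- The change-score difference estimates τ + d.

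With assumed τ = −0.40, ρ = 0.3-0.7 and d = 0.05-0.20:
- ANCOVA: −0.40 + 0.3 × 0.05 = −0.385, to −0.40 + 0.7 × 0.20 = −0.26
- Change score: −0.40 + 0.05 = −0.35, to −0.40 + 0.20 = −0.20

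A simulation with 200,000 subjects gave −0.38 to −0.26 and −0.35 to −0.20. The values of d are illustrative and are not derived from step 3, because the documents give no SD with which to convert a percentage.

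**5. Prime dilution across the same window.** Assuming plasma volume 2.5-3.5 L, prime 1-2 L and full mixing, a post-pump-on value is lower by prime / (plasma + prime): from 1 / 4.5 = 22% to 2 / 4.5 = 44%. This applies in both arms, so at baseline it is mainly noise unless draw timing differs by arm.

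**The case against.** The case for leaving this alone has several sound parts.

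- **The governing SAP contains no such analysis.** SAP section 1 says its analyses are those for the final report and may differ from the protocol's. A reader might infer that a planned final analysis is biased. The documents do not support that: the point applies only if the protocol's biomarker endpoints are reported. This stands.
- **Enrolment has ended.** Narrowing the window cannot change samples already drawn. This stands for this trial.
- **The 2-18% is an extreme.** It needs a draw at the very end of the window and full flow from the first second, whereas 8.5.3.1 has flow adjusted to target and accepts 300 mL/min. A reader might take 18% as typical. The uniform-draw average of 0.6-4.7% shows otherwise, although the true draw times are unknown. Section 8.5.4 and Table 4 footnote 5 describe arterial-line sampling during CPB, which points toward later draws without settling the matter.
- **A few percent of a low starting value is small.** Section 2 says pfHb is normally low and rises sharply on CPB, so the absolute shift may be minor against the later rise. This limits the size for pfHb. The documents give no starting level for C3a or C5a.
- **The direction is conservative.** A false claim of removal is not the likely result. This stands, provided the device lowers the marker.
- **The pre-induction sample may not exist for everyone.** Section 11.2.1.1 allows for increasing the number of patients who provide biomarkers, which suggests that not all do. This stands and limits the remedy.
- **An earlier baseline has its own cost.** The treated arm's device circuit is primed with saline or crystalloid (8.5.3.1), so extra dilution in that arm could pass for removal. This stands and must be stated with the remedy.

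None of this alters the timing: a compliant baseline can be post-treatment in one arm only.

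**Conclusion.** The point holds for the protocol's secondary endpoints pfHb and C3a and its exploratory endpoints C5a and the mediator panel. Their baseline, which is also the ANCOVA covariate, can follow up to 1.5-2.0 L of device flow in the treated arm and none in control. That much rests on the documents alone.

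The size does not. The removal percentages rest on assumed extraction, volume and draw timing, and the estimate ranges on an assumed effect, correlation and baseline shift. The bias is probably toward no effect and is zero for draws before pump-on.

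A reader might infer that the AKI result is affected. It is not: Table 1 sets the pre-procedure value as baseline for all endpoints other than these markers. Nor do the documents support reading dilution at baseline as a between-arm bias. The correction is worth making before any of these markers are reported, mainly because it costs so little.

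**What to change.** **If these endpoints are reported for this trial.** Add an analysis to the SAP: on-CPB concentrations by ANCOVA, with the pre-procedure (pre-induction) value as covariate, for all randomised subjects in both arms who provided it. Report the start-of-CPB value as the first on-treatment point, not as baseline. Do not substitute the earlier value only where the draw followed pump-on, since that would mix two covariates according to draw timing.

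**For any further sampling or a successor protocol.** Require the start-of-CPB draw for these markers before device flow opens, with a window of −5 to 0 minutes.

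**Cost.** A line or two of analysis text and one window edit, with no new blood samples and no change to the sample size. Three downsides should be stated:
- The pre-procedure value misses changes between induction and pump-on.
- Prime dilution, including any extra device-circuit prime in the treated arm, becomes part of the on-CPB difference and should be noted when interpreting removal.
- Some draws may fall outside the narrower window.
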